## STATEMENT OF COMPLIANCE

The trial will be carried out in accordance with International Conference on Harmonisation Good Clinical Practice (ICH GCP) and the following:

- United States (US) Code of Federal Regulations (CFR) applicable to clinical studies (45 CFR Part 46, 21 CFR Part 50, 21 CFR Part 56, 21 CFR Part 312, and/or 21 CFR Part 812)

National Institutes of Health (NIH)-funded investigators and clinical trial site staff who are responsible for the conduct, management, or oversight of NIH-funded clinical trials have completed Human Subjects Protection and ICH GCP Training.

The protocol, informed consent form(s), recruitment materials, and all participant materials will be submitted to the Institutional Review Board (IRB) for review and approval. Approval of both the protocol and the consent form must be obtained before any participant is enrolled. Any amendment to the protocol will require review and approval by the IRB before the changes are implemented to the study. In addition, all changes to the consent form will be IRB-approved; a determination will be made regarding whether a new consent needs to be obtained from participants who provided consent, using a previously approved consent form.]

## 1 PROTOCOL SUMMARY

### 1.1 SYNOPSIS

**Title:** Phase II Trial Evaluating the Efficacy of Moderna COVID-19 Vaccine Booster Dosing in Patients with Hematologic Malignancies Who Did Not Have an Adequate Response to Prior Vaccination

**Study Description:** Patients with multiple myeloma, AL amyloidosis, or other hematologic cancers who have not had a strong positive serologic response to prior anti-COVID-19 vaccination will be given a single booster dose of the Moderna mRNA COVID-19 vaccine, and serologic response will be measured 28 days (+/- 3 days) later.

**Objectives:** Primary Objective: To determine whether booster dosing with the Moderna COVID-19 vaccine can induce humoral immune responses in patients with hematologic malignancies who did not have an adequate response to prior first vaccination with any of the SARS-CoV2 vaccines authorized for use in the USA.

Secondary Objectives:

1. To determine whether booster dosing with the Moderna COVID-19 vaccine is safe in patients with multiple myeloma, AL amyloidosis, or other hematologic malignancies.
2. To compare the humoral immune responses between the patients who had a WEAK POSITIVE RESPONSE to prior vaccine (Cohort 3) vs. those with NO RESPONSE to prior vaccination (Cohorts 1 and 2).
3. To descriptively summarize clinical and immune characteristics which contribute to likelihood of responding to booster dosing with the Moderna COVID-19 vaccine.

**Endpoints:**

Primary Endpoint:

The primary endpoint is the observed rate of anti-SARS-CoV2 IgG antibody seroconversion (from negative to positive) measured 28 days (+/- 3 days) following a booster dose of the Moderna mRNA COVID-19 vaccine.

Secondary Endpoints:

1. AEs and SAEs observed in participants, determined according to daily phone calls or video chats for 1 week following vaccine administration, and then weekly after that until 4 weeks after vaccination (Pts will also be examined 4 weeks after vaccination).
2. The observed rate of anti-SARS-CoV2 IgG antibody seroconversion (from negative to positive) measured 28 days (+/- 3 days) following a booster dose of the Moderna mRNA COVID-19 vaccine
- 3.a. Clinical characteristics of enrolled participants, including treatment history, disease, status, or presence of immunoparesis (i.e., hypogammaglobulinemia)
- 3.b. Characterization of other aspects of patients' immune status through T-cell profiling, including analysis of T-cell receptor (TCR) reactivity against COVID-19 antigens

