### 3 OBJECTIVES AND ENDPOINTS

OBJECTIVES	ENDPOINTS	JUSTIFICATION FOR ENDPOINTS
Primary		
To determine whether booster dosing with the Moderna COVID-19 vaccine can induce humoral immune responses in patients with hematologic malignancies who did not have an adequate response to prior first vaccination with any of the SARS-CoV2 vaccines authorized for use in the USA.	The primary endpoint is the observed rate of anti-SARS-CoV2 IgG antibody seroconversion (from negative to positive) measured 28 days (+/- 3 days) following a booster dose of the Moderna COVID-19 vaccine.	The described assay measures antibodies against the SARS-CoV2 spike protein, which is what the Moderna vaccine is designed to induce. This is a commercially available assay which is already in use at the Karmanos Cancer Center and Detroit Medical Center.
Secondary		
1. To determine whether booster dosing with the Moderna COVID-19 vaccine is safe in patients with multiple myeloma, AL amyloidosis, or other hematologic malignancies.  2. To compare the humoral immune responses between the patients who had a WEAK POSITIVE RESPONSE to prior vaccine (Cohort 3) vs. those with NO RESPONSE to prior vaccination (Cohorts 1 and 2).  3. To descriptively summarize clinical and immune characteristics which contribute to likelihood of	1. AEs and SAEs observed in participants, determined according to daily phone calls or video chats for 1 week following vaccine administration, and then weekly after that until 4 weeks after vaccination (Pts will also be examined 4 weeks after vaccination).  2. Humoral immune responses measured 28 days (+/- 3 days) following a booster dose of the Moderna COVID-19 vaccine.  3.a. Clinical characteristics of enrolled participants, including treatment history, disease, status, or presence	This is an early experience with booster dosing using the Moderna COVID-19 vaccine. Though new AEs/SAEs are not expected, it is important to document the safety of this intervention.  Clinical factors related to disease or immune status may be associated with likelihood of responding to booster

OBJECTIVES	ENDPOINTS	JUSTIFICATION FOR ENDPOINTS

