## 4 STUDY DESIGN

### 4.1 OVERALL DESIGN

The specific hypothesis being tested is that it may be possible to induce a protective humoral immune response with a booster dose of the Moderna COVID-19 vaccine in patients with hematologic malignancies who did not have an adequate response to first vaccination with any of the available COVID-19 vaccines. To test this hypothesis, the Karmanos Cancer Institute will conduct a Phase II single-stage trial in which patients with a negative or weak positive anti-SARS-CoV2 IgG antibody test (defined as <1.00 S/CO and 1.00-1.99 S/CO, respectively) will receive a single standard dose of the Moderna COVID-19 vaccine intramuscularly, and then have anti-SARS-CoV2 IgG antibody levels checked 28 days (+/-3 days) later. This will be a single institution trial which will be open to enrollment at the Detroit (Dresner) and Farmington Hills (Weisberg) treatment facilities. As this is an open label Phase 2 trial, there is no randomization or stratification involved. There will be three cohorts enrolled: a cohort of MM and AL amyloidosis patients with an anti-SARS-CoV2-IgG Ab level of <1.0 S/CO, a cohort of patients with other hematologic malignancies (HM) with an anti-SARS-CoV2-IgG Ab level of <1.0 S/CO and a mixed MM/AL/HM cohort in which patients have an anti-SARS-CoV2-IgG Ab level of 1.0-1.99 S/CO ("low-positive cohort"). Each cohort will be of sufficient size to evaluate the efficacy of the intervention separately, and all secondary endpoints will be analyzed on the entire combined patient set.

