### 5 STUDY POPULATION

#### 5.1 INCLUSION CRITERIA

In order to be eligible to participate in this study, an individual must meet all of the following criteria:

1. Provision of signed and dated informed consent form
2. Stated willingness to comply with all study procedures and availability for the duration of the study
3. Male or female, aged 18 years of age or older
4. Previously diagnosed with MM/AL amyloidosis (Cohorts 1 or 3) or other hematologic malignancy (Cohorts 2 or 3).
5. Previously received any one of the available COVID-19 vaccines (between 4 and 36 weeks prior to enrollment)
6. Anti-SARS-CoV2 IgG antibody titer of results less than 1.0 units (Cohorts 1 and 2), or 1.0-1.99 units (Cohort 3). Antibody titers will be measured within 14 days of enrollment.
7. If currently receiving potentially immunosuppressive anti-neoplastic therapy for their underlying hematologic condition, a two-week interruption in therapy before and after the booster dose of vaccine is ENCOURAGED BUT NOT REQUIRED (physician discretion).

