## 9.2 END POINTS

The primary and second secondary endpoints are the observed response rate of anti-SARS-CoV2 IgG antibody seroconversion (positive vs. negative) measured 28 days (+/- 3 days) following a booster dose of the Moderna mRNA COVID-19 vaccine.

The first secondary endpoints are AEs and SAEs observed in participants, determined according to daily phone calls or video chats. The third secondary endpoints are (a) clinical characteristics of enrolled participants, including treatment history, disease, status, or presence of immunoparesis (i.e., hypogammaglobulinemia) and (b) characterization of patients' immune status through lymphocyte subset profiling, cytokine level analysis, and assessment of immune exhaustion markers.

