## 9.3 SAMPLE SIZE DETERMINATION

The specific hypothesis being tested is that it may be possible to induce a protective humoral immune response with a booster dose of the Moderna COVID-19 vaccine in patients with hematologic malignancies who did not have an adequate response to first vaccination with any of the available COVID-19 vaccines. The null hypothesis is that 5% or less of patients who have an anti-SARS-CoV2-IgG Ab titer of less than 2.0 S/CO will spontaneously develop a higher titer. We hypothesize that at least 15% of patients in each cohort will develop a titer of 2.0 S/CO or greater in response to the vaccine, without toxicity in excess of that previously described amongst COVID-19 vaccine recipients.

Thus, the sample size for each cohort of this trial was determined using the Phase 2 single-arm single-stage design based on the following statistical assumptions:  $p_0=5\%$ ,  $p_1=15\%$ , 1-sided alpha = 5%, and power = 80%. In this case, 52 patients would be enrolled to each of the three cohorts. In each cohort, at least 6 patients would need to develop an anti-SARS-CoV2-IgG Ab titer of  $>2.0$  S/CO to reject the null hypothesis. Therefore, a total of 156 response-evaluable patients would be enrolled in this 3-parallel cohort, single-arm, single-stage Phase 2 trial. Given that the study intervention is a single vaccination, and the primary endpoint requires a single visit for a physical a blood sample collection, there should be relatively few non-evaluable patients. Patients who are non-evaluable for the primary endpoint will be replaced only if it becomes evident that this is needed to determine whether or not the primary endpoint is met in any/all of the cohort(s). We expect this will amount to no more than 5 additional patients in any of the three cohorts, so the maximum number of enrolled participants is 171 (= 57 x 3 cohorts).

The size of the trial will also permit a comparison of the likelihood of developing a strong positive response amongst the pooled participants form Cohorts 1 and 2 (i.e., the participants with NO RESPONSE to prior vaccination) versus the participants in Cohort 3 (i.e., the patients who had a WEAK POSITIVE RESPONSE to prior vaccine) as the second secondary objective. We hypothesize that the absolute difference in response rate between Cohort 3 vs. Cohort 1+2 is 20% or more against the response rate of 15% in Cohort 1+2 (i.e., Cohort 3: 35% vs. Cohort 1+2: 15%). The sample sizes of 156

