(Cohort 3: 52 vs. Cohort 1+2: 104) will achieve 82.7% power to detect a difference of 20% between two groups at a 1-sided 5% level when the Fisher's exact test is used.

Each cohort in the primary object will be tested at a 1-sided 5% level and the second secondary objective will be also evaluated at a 1-sided 5% level. No correction for multiple comparison is planned between these primary and second secondary objectives

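### The primary endpoint is worded as conversion from negative to positive, but the design tests a titre of 2.0 S/CO; as worded, no Cohort 3 patient can respond

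*Combined protocol and SAP*

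**What the plan says.** The plan describes response in several ways.

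- **Synopsis (1.1) and Section 3.** The Synopsis gives the primary endpoint as "the observed rate of anti-SARS-CoV2 IgG antibody seroconversion (from negative to positive) measured 28 days (+/- 3 days"), and uses the same wording for the second secondary endpoint. Section 3 reads: "The primary endpoint is the observed rate of anti-SARS-CoV2 IgG antibody seroconversion (from negative to positive) measured 28 days (+/- 3 days"). Section 3 gives the second secondary only as humoral immune responses.
- **Section 4.1.** Enrolment is of "patients with a negative or weak positive anti-SARS-CoV2 IgG antibody test (defined as <1.00 S/CO and 1.00-1.99 S/CO, respectively"). Negative and weak positive are therefore separate categories.
- **Section 5.1, criterion 6.** Entry requires a titre of "less than 1.0 units (Cohorts 1 and 2), or 1.0-1.99 units (Cohort 3").
- **Section 9.2.** The primary and second secondary endpoints are both "seroconversion (positive vs. negative) measured 28 days (+/- 3 days) following a booster dose of the Moderna mRNA COVID-19 vaccine". There is no cut-off and no stated change from baseline.
- **Section 9.3.** The hypothesis is that "at least 15% of patients in each cohort will develop a titer of 2.0 S/CO or greater in response to the vaccine". The rejection rule asks for at least 6 patients per cohort above 2.0 S/CO. The second secondary objective is a "comparison of the likelihood of developing a strong positive response amongst the pooled participants form Cohorts 1 and 2" against Cohort 3, and 52 versus 104 patients "will achieve 82.7% power to detect a difference of 20% between two groups at a 1-sided 5% level".
- **Section 9.4.1.** The variable analysed for both objectives is a response rate, which the section identifies with the primary endpoint. It states no threshold.

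**The concern.** The sections that define the endpoint and the section that sizes the trial describe different events. Cohort 3 is made up entirely of patients at 1.0-1.99 S/CO, so an event that must start from negative cannot occur there. Yet Section 9.3 applies the 6-of-52 test to that cohort and expects it to respond more often than the other two (35% against 15%).

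In Cohorts 1 and 2, a patient who moves from below 1.0 to 1.0-1.99 has left the negative category and can be counted as a conversion. The Section 9.3 rule does not count that patient.

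At stake are the three primary tests and the only powered secondary comparison. The trial is open label, and Section 10.1.6 has response reported to the monitoring committee every month. A threshold settled during the analysis would therefore be chosen after titres were known.

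**Working it through.** **Inputs.** From Section 9.3: p0 = 5%, p1 = 15%, one-sided alpha 5%, power 80%, n = 52 per cohort, reject at 6 or more; 35% (Cohort 3, n = 52) against 15% (Cohorts 1+2, n = 104), Fisher's exact test, one-sided 5%. From Section 4.1: negative is below 1.00 S/CO. From criterion 6: Cohort 3 baseline is 1.0-1.99.

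**1. The plan's own figures (2.0 S/CO definition).** With X ~ Binomial(52, p):

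- P(X ≥ 6 | p = 0.05) = 0.0445
- P(X ≥ 6 | p = 0.15) = 0.8119

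With n = 51 and the same cut-off, power is 0.797. A search over n confirms 52 as the smallest exact design. Full enumeration of the one-sided Fisher test at 35% of 52 against 15% of 104 gives power 0.833, close to the stated 82.7%. The design arithmetic holds.

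**2. Cohort 3, endpoint as worded.** Every baseline value is at least 1.0, so the conversion probability is 0.

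- Observed result: 0/52, and P(X ≥ 6) = 0 instead of 0.8119
- Exact 90% CI upper limit: 1 − 0.05^(1/52) = 0.056

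**3. Second secondary comparison, endpoint as worded.** Compare 0/52 in Cohort 3 with b/104 in Cohorts 1+2.

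- One-sided p in favour of Cohort 3: P(X ≥ 0) = 1.00 for every b, so power is 0.
- One-sided p in the opposite direction: C(104, b)/C(156, b), which is 0.0546 at b = 7 and 0.0355 at b = 8.
- P(b ≥ 8 | n = 104, p = 0.15) = 0.992.

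The 15% is the planning rate for reaching 2.0 S/CO. A patient who goes from below 1.0 to 2.0 has also crossed 1.0, so the rate of crossing 1.0 cannot be lower, and 0.992 is a floor given that planning rate.

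**4. Section 9.2 read as Day-28 status at a 1.0 cut-off.** Cohort 3 now fails the other way, because an unchanged patient counts as a responder. The documents give no rate for staying at or above 1.0 without a vaccine effect, so these rates are assumed:

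| Assumed rate at or above 1.0 | P(X ≥ 6 of 52) |
|---|---|
| 20% | 0.9631 |
| 25% | 0.9952 |
| 30% | 0.9996 |

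**5. Cohorts 1 and 2 if 6 of 52 is applied to crossing 1.0.** The documents give no null rate for this event. The 5% in Section 9.3 refers to 2.0 S/CO. Adding an assumed share that lands in 1.0-1.99 without a vaccine effect gives:

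| Assumed null rate of crossing 1.0 | P(X ≥ 6 of 52) |
|---|---|
| 5% (no extra) | 0.0445 |
| 6% | 0.0901 |
| 7% | 0.1544 |
| 8% | 0.2345 |
| 10% | 0.4208 |

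This inflation does not arise under the Section 9.3 rule as written.

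**The case against.** The strongest reply is that Section 9.3 already settles the matter. Its rejection rule names 2.0 S/CO for each cohort, and its 35% assumption for Cohort 3 shows that a zero rate was never meant. Section 9.4.1 speaks of a response rate, the term Section 9.3 uses for the Cohort 3 comparison. The Synopsis describes the population as lacking a strong positive response, which fits reading response as strong positive. Section 3 puts no negative-to-positive condition on the second secondary endpoint, so the reversed comparison does not follow from that section. The reverse-direction test is not in the plan, and the rates in steps 4 and 5 have no source in it.

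Much of this stands. The intended threshold was most likely 2.0 S/CO, the sample size is unaffected, and steps 4 and 5 are illustrations only.

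It does not remove the conflict. Section 9.4.1 says that the response rate used for both objectives is the primary endpoint, and Section 9.2 makes the primary and second secondary endpoints the same, so the endpoint wording carries into the comparison. Reading negative as anything below 2.0 contradicts Section 4.1, and the objectives likewise separate no response from weak positive. In Cohorts 1 and 2 both readings give believable but different counts, so common sense would not expose the error there as it would with 0/52.

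**Conclusion.** The concern holds. The plan gives incompatible definitions of its primary endpoint, and the one in the Synopsis and Section 3 cannot be met in one of the three primary cohorts. That result (0/52, upper limit 5.6%, no chance of reaching 6) follows from the plan's own definitions and needs no outside assumption. Carried into the second secondary comparison, the same wording gives power 0 in the planned direction. It also produces data favouring Cohorts 1+2 at the one-sided 5% level in at least 99.2% of trials, if those cohorts reach 2.0 S/CO at the planned 15%.

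For Cohorts 1 and 2 the effect depends on how many patients cross 1.0 S/CO without a vaccine effect, which the documents do not say. At assumed rates of 6% to 10%, the 6-of-52 rule applied at that cut-off would reject falsely in about 9% to 42% of trials, against 4.45% at the planned threshold. The defect is in the endpoint definition, not in the design calculation, and it should be corrected before any efficacy analysis.

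**What to change.** - In Sections 1.1, 3, 9.2 and 9.4.1, define the primary and second secondary endpoint as a Day-28 (±3 days) titre of 2.0 S/CO or greater in a patient whose screening titre was below 2.0 S/CO.
- In Section 9.3, change the rejection rule from above 2.0 to 2.0 or greater, so that it matches the hypothesis and a value of exactly 2.0 is classified one way.
- If conversion across 1.0 S/CO is of interest, report it descriptively and for Cohorts 1 and 2 only.
- As tidying, align the cohort ranges in the Synopsis with the below-1.0 and 1.0-1.99 ranges in Section 4.1 and criterion 6.

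The cost is a text amendment with the usual IRB review. The 52 patients per cohort, the cut-off of 6, the assay and the visit schedule stay as they are.

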**Study Population:**

Three 52-person cohorts. Cohort 1: multiple myeloma and amyloidosis patients who did not develop an anti-spike antibody titer of >1 S/CO after prior COVID-19 vaccination. Cohort 2: patients with other hematologic malignancies who did not develop an anti-spike antibody titer of >1 S/CO after prior COVID-19 vaccination. Cohort 3: patients with multiple myeloma, amyloidosis, or other hematologic malignancy who had a "weak positive" response to prior COVID-19 vaccine, defined as an anti-spike antibody titer of 1-2 S/CO. Patients with a history of severe prior adverse vaccine reaction are excluded. Patients must be 18 yo or older.

**Phase:**

Phase 2

**Description of**

**Sites/Facilities Enrolling** The Karmanos Cancer Institute (Dresner and Weisberg Facilities)  
**Participants:**

[figure not shown]
**Description of Study Intervention:** A single “booster” dose of the Moderna mRNA COVID-19 vaccine will be administered intramuscularly

**Study Duration:** All participants will be dosed within 3 months of the trial opening, and the primary endpoint will be assessed in all participants by 28 days (+/- 3 days) of the last participant being dosed. Thus, the expected study duration is ~10 months (factoring in ~2-month accrual duration and also ~4-months each for IRB approval and data analysis)

**Participation Duration:** 6-8 weeks

## 1.2 SCHEMA

### ***Flow diagram***

### 1.3 SCHEDULE OF ACTIVITIES (STUDY CALENDAR)

Procedures	Screening/Consenting Day -14 to -1	Enrollment/Baseline Visit 1, Day 1	Days 2-8, 15, 22 (+/- 1 day) Phone/Text/Email	Study Visit 2 Day 28 +/- 3 days
Informed consent	X			
Demographics	X			
Medical history update	X			X
Administer vaccine dose		X		
Concomitant medication review	X			X
Physical exam	X			X
Vital signs	X	X		X
Height	X			
Weight	X			X
Performance status f	X			X
Hematology a	X			X
Serum chemistry b	X			X
Cardiac Biomarkers e	X		(X) d	X
Coagulation testing c	X			
Anti-SARS-CoV2 IgG Ab titer	X			X
Patient-reported AE assessment		X	X---X	X
Correlative blood sample collection	X			X

a. CBC with diff  
b. standard CMP, uric acid, magnesium, phosphorus, LDH, quantitative immunoglobulins (IgG, IgA, IgM)  
c. PT/INR, PTT, fibrinogen  
d. only if patient reports chest pain, palpitations, shortness of breath, or other symptoms suggesting cardiac etiology  
e. hsTrop I and BNP  
f. See Appendix 1: ECOG Performance Status

## 2 INTRODUCTION

### 2.1 STUDY RATIONALE

While vaccines authorized for emergency use to prevent severe acute respiratory syndrome coronavirus 2 (SARS-CoV2) infection provide most recipients resistance to SARS-CoV2 infection, it has become clear that immunocompromised patients (including solid organ transplant recipients, patients on therapy for autoimmune diseases, and people with hematologic malignancies such as multiple myeloma and chronic lymphocytic leukemia) may not mount an adequate humoral immune response after a standard initial vaccine course. There is no consensus on how to approach such patients. This trial will examine whether administration of booster doses of an authorized SARS-CoV2 vaccine can induce an immune response in such patients with hematologic malignancies.

